10.1.12.4 PROTOCOL COMPLIANCE

Study personnel will be required to pass a general knowledge assessment prior to trial implementation. If deviations to the protocol occur, the event and a description of it will be reported to the CC (see section 10.1.9). The CC may observe study visits during in-person site monitoring visits to verify adherence to the protocol.

10.1.12.5 TRIAL SAFETY

A masked medical monitor at the CC has been appointed to evaluate the safety of the trial. All serious adverse events experienced by enrolled patients will be reported to the medical monitor in a timely manner, as defined in section 8.3.6. The medical monitor will determine expectedness of the patient's treatment and the reported event. The medical monitor will report his findings to the relevant entities defined in section 8.3.6.

The NEI's appointed DSMC will also review serious adverse events and general trial data on a 6-month basis, or as deemed necessary. Progress reports will be prepared for all scheduled DSMC meetings. An interim analysis will be performed and presented to the DSMC by the trial's unmasked biostatistician when approximately 40% of the trial's anticipated events have occurred. Whether or not to continue the trial will be based on this interim analysis. See **SAP section 3.7** for details on stopping.

On February 14th, 2024 the DSMC met, stopped enrollment and provided the following guidance for patients still completing follow-up in the trial:

- Patients should be told by the study investigator the results regarding efficacy of the continued administration of adalimumab for preventing recurrence of uveitis or arthritis.
- Patients are encouraged to remain in their assigned treatment group and complete follow-up, per protocol.
- Patients in active follow-up who have not yet been unmasked to their treatment assignment can be asked if they want to know their current treatment assignment.
- Patients receiving placebo may opt to discontinue their injections.

10.2 ABBREVIATIONS

AC	Anterior Chamber
ADA	Anti-drug Antibodies (to adalimumab)
AE	Adverse Event
BCVA	Best-corrected Visual Acuity
CAU	Chronic Anterior Uveitis
CC	Coordinating Center
CFR	Code of Federal Regulations
CONSORT	Consolidated Standards of Reporting Trials
CRF	Case Report Form
CRP	C-reactive Protein
DSMC	Data and Safety Monitoring Committee
FDA	Food and Drug Administration
ESR	Erythrocyte Sedimentation Rate
GCP	Good Clinical Practice
GMP	Good Manufacturing Practices
ICF	Informed Consent Form
ICH	International Conference on Harmonisation
ID	Identification
IND	Investigational New Drug Application
IRB	Institutional Review Board
JIA	Juvenile Idiopathic Arthritis
MOP	Manual of Operating Procedures
NEI	National Eye Institute
NIH	National Institutes of Health
OCT	Optical Coherence Tomography
OHRP	Office for Human Research Protections
PDF	Portable Document Format
PI	Principal Investigator
QC	Quality Control
SAE	Serious Adverse Event
SAP	Statistical Analysis Plan
SMC	Safety Monitoring Committee
SOA	Schedule of Activities
SOP	Standard Operating Procedure
TGS	Therapeutic Goods Administration
TNF	Tumor Necrosis Factor
UCSF	University of California, San Francisco
UK	United Kingdom
UP	Unanticipated Problem
US	United States

10.3 PROTOCOL AMENDMENT HISTORY

Version	Date	Description of Changes
1.1	22 October 2019	
 1. Corrected the formulation of the study medication (adalimumab and placebo) being donated by AbbVie (Section 6.2.2) 2. Updated Section 6.2.3 to include required language by AbbVie on study medication storage and stability
1.2	10 April 2020	
 1. Removed the Baseline Medication Form (Section 1.3) 2. Clarified that there must be at least 28 days between the two consecutive study visits before the study medication dose can be increased to 40 mg due to a weight increase (Section 4.3) 3. Expanded permitted concomitant antimetabolites to azathioprine and leflunomide (Sections 4.3, 5.1, and 6.5.2) 4. Extended the time period of which a planned intraocular surgery would disqualify a patient from 180 days to 12 months (Section 5.2) 5. Added that the use of NSAID eye drops within the past 90 days prior to enrollment would disqualify a patient (Section 5.2) 6. Clarified that prior attempts at discontinuing adalimumab or other TNF-α inhibitors do not disqualify a patient (Section 5.2) 7. Clarified that patients who are prescribed oral corticosteroids for conditions unrelated to JIA are still eligible (Sections 5.2 and 6.5.3) 8. Removed that patients will bring back unused pre-filled syringes of study medication to assess for medication adherence. Adherence will be measured through patient self-report alone (Section 6.4) 9. Added that patients will be assessed on their perception of randomized treatment group prior to unmasking (Section 8.2) 10. Included age thresholds for obtaining assent/consent from patients and their parents in Australia (Section 10.1.1)
1.3	21 October 2020	
 1. Updated study duration (Section 1.1) 2. Clarified time window for the Baseline laboratory measurements (Section 1.3) 3. Specified a time window for when a rheumatology exam and a standard of care blood draw do not need to be reperformed at a treatment failure visit if recently conducted (Section 1.3) 4. Added The Children's Hospital at Westmead and Queensland Children's Hospital as enrolling centers in Australia (Sections 4.1 and 5.5) 5. Added that route of concomitant antimetabolite administration (injectable or oral methotrexate, mycophenolate mofetil, azathioprine, or leflunomide) must remain stable for ≥ 90 days (Sections 4.3 and 5.1) 6. Clarified the type of JIA-associated uveitis that can be enrolled (Section 5.1) 7. Added that an additional anti-adalimumab antibody sample may be collected post treatment failure per investigator's discretion (Section 8.1)

		
 8. Updated F.I. Proctor Foundation address to Mission Bay location ([name]) (Section 10.1.4)
1.4	22 April 2021	
 1. Updated address of Colorado Retina Associates as it moved to Lakewood, CO. (Section 4.1 and 5.5) 2. Reduced the recency requirement for screening labs for patients not on an antimetabolite, from within 90 days, to within 180 days. If on an antimetabolite, then screening labs recency requirement remains within the past 90 days. (Section 5.3) 3. Reduced the frequency requirement for standard of care labs to every 6 months for patients not taking an antimetabolite. For patients prescribed an antimetabolite, there is no change to the frequency of standard of care labs conducted. (Section 1.3, 5.3, and 8.2) 4. Removed the requirement for patients to return empty/used treatment kits to the study coordinator. (Section 6.4) 5. Removed the inclusion criteria regarding a negative tuberculosis test within the past 12 months (Section 5.1) Added tuberculosis testing at Baseline (if a test has not been completed in the 12 months prior), and general guidance for responding to an indeterminate or positive result. (Section 8.2)
1.5	01 October 2021	
 1. Changed the number of active sites in the synopsis (Section 1.1) 2. Added an explanation about ANA-positive chronic anterior uveitis (CAU) to the synopsis, study background, and study rationale. (Section 1.1, 2.1, and 2.2) 3. Changed the inclusion criteria to include CAU in juveniles (presenting <16 years old) (Section 5.1) 4. Added CAU when describing JIA-associated uveitis in various descriptions throughout the document including the objectives, study design, exclusion criteria, recruitment, and statistical analysis sections (Sections 3, 4, 5.2, 5.5, and 9.4) 5. Added a description that CAU will be treated identically to JIA in regard to rheumatology visits (Section 7.1) 6. Added plan for subgroup analysis of patients with and without JIA (Section 9.4.6) 7. Incorporated patient-centered language throughout the document, describing “patients with JIA or CAU” instead of “JIA and CAU patients”.
1.6	01 April 2022	
 1. Added presence of intraretinal or subretinal fluid as exclusion criteria (Section 5.2) 2. Clarified that occurrence of vitreous haze, retinal or choroidal inflammation, or macular edema at a single visit constitutes treatment failure. (Section 3.0) 3. Clarified the criteria for macular edema as a CST of 2 standard deviations greater than the mean and having a greater than 20% increase in CST from baseline, and/or having intraretinal or subretinal fluid on the OCT scan (sections 3.0, 4.2, 6.5, 7.1)

		
 4. Added University Hospital of Leicester and Meyer Children's Hospital in Florence as study sites and removed Duke University and Johns Hopkins Wilmer Eye Institute (sections 4.1, 5.5) 5. Changed number of enrollment centers to include Italy and included them in the consent procedures and study closure (sections 1.1, 5.5, 10.1.1.2, 10.1.2) 6. Added the Good-Lite machine as an acceptable alternative for the EVA device (section 8.1)
1.61	28 September 2022	
 1. Removed ANA positivity requirement for CAU (sections 1.1, 2.1, 2.2, 5.1, 9.4.5) 2. Removed Meyer Children's Hospital in Florence as a study site (sections 4.1, 5.5) 3. Changed number of enrollment centers to remove Italy and included them in the consent procedures and study closure (sections 1.1, 4.1, 10.1.1.2, 10.1.2)
1.7	27 June 2023	
 1. Removed Seattle Children's Hospital, Spokane Eye Center, Children's Hospital at Westmead, Queensland Children's Hospital, and University Hospitals Southampton as study sites (sections 4.1, 5.5) 2. Changed number of enrollment centers to remove Seattle Children's Hospital, Spokane Eye Center, Children's Hospital at Westmead, Queensland Children's Hospital, and University Hospitals Southampton (sections 1.1, 4.1, 5.5) 3. Added 70-day post trial Adverse Event phone call to the study visit schedule (section 1.3) 4. Specified when the interim analysis would take place and revised the section number to correspond with the updated SAP (section 10.1.12.5) 5. Clarified abnormal lab exclusion criteria (section 5.2) 6. Stated the assessments that will be conducted at the 90-day follow-up visit for patients who experience late treatment failure (section 1.3, 4.4) 7. Removed age cap for quality of life questionnaire (section 8.1)
1.8	14 February 2024	
 1. Clarified which Treatment Assessment Form to fill out before/after treatment failure. (section 1.3) 2. Included Treatment Failure Criteria table instead of referring to the MOP, for ease of reference. (section 3.1) 3. Removed 3 repetitive footnotes. (sections 3.1, 4.2, 6.5.1, 7.1) 4. Clarified list of acceptable OCT imaging machines. (section 8.1) 5. Referred to the Statistical Analysis Plan for all statistical considerations (section 3, 9) 6. Included more details about our Good Clinical Practice and Human Subjects Research certification requirements. (section 10.1.12) 7. Added DSMC's recommendation for Investigators to discuss the Interim Analysis results with every patient and give masked patients the opportunity to unmask. (section 10.1.12.5)

This Statistical Analysis Plan (SAP) describes the planned analyses for the ADalimumab in Juvenile idiopathic arthritis-associated Uveitis Stopping Trial (ADJUST). It includes specifications for the statistical analyses and the tables to be prepared for the interim analyses and final Clinical Study Report.

This SAP conforms to the guidelines for Statistical Analysis Plans released by the Society for Clinical Trials and is in accordance with recently published “Guidelines for the Content of Statistical Analysis Plans in Clinical Trials” in JAMA.¹ The background for this SAP can be found in the ADJUST Manual of Operations (MOP).

The planned analyses in this SAP will be included in future manuscripts. Exploratory analyses not expressly identified here may still be performed but will be clearly documented as such in the final Clinical Study Report.

The final SAP is subject to the approval of an appointed Data and Safety Monitoring Committee.

2 Investigational Plan

2.1 Study Design

This study is a multicenter, randomized, double-masked, Phase IV superiority clinical trial to evaluate the efficacy of adalimumab withdrawal in patients with controlled JIA-associated uveitis.

2.2 Study Population

Eligible patients will have controlled JIA-associated uveitis or chronic anterior uveitis (CAU) on adalimumab with no other suspected etiology of uveitis. Complete inclusion and exclusion criteria are given in ADJUST Manual of Operations Section 3.3.²

2.3 Specific Aims

2.3.1 Specific Aim 1

Primary Outcome of the trial. The primary outcome for Specific Aim 1 will be time to treatment failure, with censoring at 12 months. Treatment failure occurs when recurrence of ocular inflammation is observed and/or the recurrence of joint inflammation is persistent and severe enough to necessitate unmasking to manage the arthritis recurrence. The recurrence of ocular inflammation is defined as one or more of the features in Table 1 in at least one eye:

Table 1: Criteria for Treatment Failure by Uveitis Recurrence
(at least one of the following in at least one eye)

Parameter	Definition
Anterior chamber cells*	≥2-step increase** at two separate visits ≥7 days apart >0.5+ cell observed for ≥28 days ≥3+ cell observed at a single visit
Vitreous haze***	>0.5+ haze at a single visit
Choroid & retina	Active retinal / choroidal lesions or macular edema (CST >2 standard deviations above normal thickness or cysts in 1mm central subfield) at a single visit

*SUN criteria³, **increase is based on inflammation at baseline; ***NEI vitreous haze grading scale⁴

Secondary Objectives

- To compare the proportion of people exhibiting treatment failure between the randomization groups during the first 6 months and during the first 12 months of study duration.
- To compare the cost-effectiveness of adalimumab therapy between the randomization groups during 12 months.

Secondary Objectives with Alternative Outcomes

We propose to compare longitudinal values of specific variables between the two randomization groups. The following outcomes will be compared:

- Best Corrected Visual Acuity (BCVA) score,
- Childhood Health Assessment Questionnaire score (CHAQ)⁵ in patients ages 5+,
- EuroQol 5 Dimension Youth Survey (EQ-5D-Y)⁶ score in patients ages 4+,
- Children's Visual Functioning Questionnaire (CVFQ)⁷ score in children aged 3 to 7 years,
- Effects of Youngster's Eyesight on Quality of Life (EYE-Q)⁸ score in children ages 5+,
- Juvenile Arthritis Disease Activity Score (JADAS)⁹ values: JADAS-10 and JADAS-27,
- Estimates of anti-adalimumab antibody (ADA) levels.

We also propose to compare proportions between the two randomization groups. These proportions correspond to the time until treatment failure or censoring time of 6 months as well as until treatment failure or censoring time of 12 months. Specifically:

- The proportion of patients who exhibit an arthritis flare, as defined in the Manual of Operations Section 6.4.1.²
- The proportion of patients who achieve an improvement in JADAS-10 as defined by Horneff et al.⁹ The criteria for a significant improvement is as follows:
 - For patients with a baseline JADAS-10 value ≤ 15 , a decrease of 4.
 - For patients with a baseline JADAS-10 value > 15 and ≤ 25 , a decrease of 10.
 - For patients with a baseline JADAS-10 value > 25 , a decrease of 17.
- The proportion of patients exhibiting macular edema.

2.3.2 Specific Aim 2

Primary Outcome: The principal outcome for Specific Aim 2 will be occurrence of

treatment failure (as defined in Section 2.3.1) in the first 6 months and in the first 12 months.

Secondary Objectives

- To determine the predictors of uveitis recurrence (treatment failure by ocular inflammation recurrence as defined in Table 1)
- To determine the predictors of time to treatment failure (as defined in Section 2.3.1) with censoring at 6 months and with censoring at 12 months,
- To determine the predictors of BCVA at 6 and 12 months,
- To determine the predictors of arthritis flare occurrence (as defined in MOP Section 6.4.1) in the first 6 months and in the first 12 months,
- In patients ages 5+, to determine the predictors of CHAQ score at 6 and 12 months.

Supplemental Objectives

Additional exploratory analyses will be conducted to determine predictors of additional variables:

- Number of missed treatment doses during the first 6 months, and during 12 months,
- CVFQ score in children aged 3 to 7 years at 6 and 12 months,
- EYE-Q score in children ages 5+ at 6 and 12 months,
- JADAS-10 and JADAS-27 scores at 6 and 12 months,
- Achievement of improvement in JADAS-10 (MOP Section 6.4.1) over the first 6 months, and over the first 12 months,
- Occurrence of macular edema during the first 6 months and during the first 12 months.

2.3.3 Specific Aim 3

Primary Outcome: The primary outcome for Specific Aim 3 is achievement of corticosteroid-sparing controlled ocular inflammation at months 6 and 12 following enrollment. Corticosteroid-sparing controlled ocular inflammation is defined by meeting all of the criteria in Table 2 in both eyes:

Table 2: Criteria for Corticosteroid-sparing Controlled Ocular Inflammation
(both eyes have to meet all criteria)

Parameter	Definition
Anterior chamber cells*	≤0.5+ cell
Vitreous haze**	≤0.5+ haze
Choroid & retina	No active retinal / choroidal lesions or macular edema (CST >2 standard deviations above normal thickness or cysts in 1mm central subfield)
Prednisolone acetate 1%	≤2 drops/day

*SUN criteria³; **NEI vitreous haze grading scale⁴

Secondary Objectives

- To compare BCVA at 6 months and 12 months between randomization groups,
- To compare the proportion of people exhibiting an arthritis flare (as defined in MOP Section 6.4.1) between randomization groups during the first 6 months and during the first 12 months,
- For children ages 5+, to compare the CHAQ score at 6 months and at 12 months between randomization groups.

Supplemental Objectives

- To determine the predictors of regaining control of uveitis (Table 2) at 12 months in patients randomized to placebo who have a uveitis flare (Treatment Failure by ocular inflammation recurrence as defined in Table 1),
- To compare the number of missed treatment doses over 6 months and over 12 months between randomization groups.

We propose to compare final values of specific variables between the two randomization groups. Final values correspond to the value at 6 months as well as at 12 months. We will compare the following variables:

- EuroQol 5 Dimension Youth Survey (EQ-5D-Y)⁶ score in children ages 4+,
- Children's Visual Functioning Questionnaire (CVFQ)⁷ score in children aged 3 to 7 years,
- Effects on Youngster's Eyesight on Quality of Life (EYE-Q)⁸ score in children

ages 5+,

- Juvenile Arthritis Disease Activity Score¹⁰ values: JADAS-10 and JADAS-27,
- Estimates of anti-adalimumab antibody (ADA) levels.

We also propose to compare proportions between the two randomization groups. These proportions correspond to the time until 6 months as well as until 12 months. The proportions of the following variables will be compared:

- The proportion of patients who achieve an improvement in JADAS-10 scores
- The proportion exhibiting macular edema
- The proportion of people who discontinued treatment due to intolerance
- The proportion of people who discontinued treatment due to safety

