3 OBJECTIVES AND ENDPOINTS

See the Statistical Analysis Plan (SAP) for details about the objectives, endpoints, and analysis.

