3.1 TREATMENT FAILURE

Patients can discontinue the study treatment due to lack of efficacy and be declared a treatment failure if they have recurrence of ocular inflammation and/or recurrence of joint inflammation that is persistent and severe enough to necessitate unmasking to manage the arthritis recurrence.

Ocular inflammation is defined as ≥ 2 -step increase in AC cell from baseline, observed at 2 consecutive visits at least 7 days apart; $>0.5+$ AC cell for ≥ 28 days; $\geq 3+$ AC cell at a single visit; or $>0.5+$ vitreous haze, active retinal/choroidal lesions, or macular edema at a single visit.

Macular edema is defined as central subfield thickness on OCT > 2 standard deviations above normal thickness ($>320\mu\text{m}$ on Spectralis or $>300\mu\text{m}$ on Zeiss or Topcon) and having a greater than 20% increase from baseline *and/or* presence of intraretinal or subretinal fluid.

Patients with ocular inflammation that meets one of the treatment failure thresholds should return for an evaluation to evaluate whether the increased inflammation is sustained (called the Treatment Failure visit), as close to the 7- or 28-day period as possible, but no earlier.

Criteria for recurrence of ocular inflammation (at least one of the following in at least one eye)

Parameter	Definition
Anterior chamber cells*	≥ 2 -step increase** at two separate visits ≥ 7 days apart $>0.5+$ cell observed for ≥ 28 days $\geq 3+$ cell observed at a single visit
Vitreous haze***	$>0.5+$ haze at a single visit
Choroid & retina	Active retinal / choroidal inflammation and/or macular edema in either eye at a single visit. Macular edema is defined as central subfield thickness on OCT > 2 standard deviations above normal thickness ($>320\mu\text{m}$ on Spectralis or $>300\mu\text{m}$ on Zeiss or Topcon) and having a greater than 20% increase from baseline and/or presence of intraretinal or subretinal fluid

*SUN criteria; **increase is based on inflammation at baseline⁶⁰; ***NEI vitreous haze grading scale⁶¹

Patients who meet the treatment failure threshold of ocular inflammation at Month 12 will be re-evaluated after the Month 12 visit to assess for sustained inflammation which would result in treatment failure. If inflammation is sustained at the follow-up visit, then treatment failure is declared. At this point, patients and doctors will be unmasked, and doctors can treat per best medical judgement.

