5 STUDY POPULATION

5.1 INCLUSION CRITERIA

To be eligible to participate in this study, an individual must meet all of the following criteria:

- Stated willingness to comply with all study procedures and availability for the duration of the study period
- History of JIA or CAU, diagnosed prior to 16 years of age (patient may be older than 16 at time of enrollment)^a
- ≥ 2 years of age (per FDA approval for use in children with polyarticular JIA) ^b
- Formal diagnosis of JIA-associated uveitis^c or CAU^d with no other suspected etiology
- ≥ 12 consecutive months of controlled ocular inflammation ($\leq 0.5+$ anterior chamber cell, $\leq 0.5+$ vitreous haze, and no active retinal/choroidal lesions in either eye)
- ≥ 12 consecutive months of controlled arthritis verified by a pediatric rheumatologist (see **MOP Section 3.3.1** for definition of controlled arthritis) if defined as JIA-associated uveitis
- ≥ 12 consecutive months of treatment with adalimumab^e and/or a biosimilar of adalimumab^f
- ≥ 180 days on a stable dose of adalimumab or a biosimilar of adalimumab; must be biweekly dose of no greater than 20mg (if < 30 kg) or 40mg (if ≥ 30 kg)
- If on a biosimilar of adalimumab, ≥ 90 days on the biosimilar
- If on concomitant antimetabolite (injectable or oral methotrexate, mycophenolate mofetil, azathioprine, or leflunomide), dose must be ≤ 25 mg weekly for methotrexate, ≤ 3 g daily for mycophenolate mofetil, ≤ 250 mg daily for azathioprine, or ≤ 20 mg daily for leflunomide; dose and route of administration must be stable for ≥ 90 days
- If on topical corticosteroids, dose must be ≤ 2 drops prednisolone acetate 1% or equivalent per day and stable for ≥ 90 days
- Willingness to limit consumption of alcohol during the study period
- Agreement to avoid live attenuated vaccinations
- Agreement to use highly effective contraception^g for ≥ 28 days prior to screening and throughout study period (for males and females of reproductive age)
- Suitable, in the opinion of the Investigator, to continue treatment with adalimumab or placebo per regional labeling
- No contraindications to receive adalimumab as per the local Summary of Product Characteristics (SmPC)

There are no gender, race, or ethnicity restrictions for this study.

^aPatients can be older than 16 years of age at enrollment, but original diagnosis of arthritis must have been made prior to age 16 per the clinical definition of JIA

^bAdalimumab is FDA approved for use in children ≥ 2 years of age

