5.2 EXCLUSION CRITERIA

Any one of these excludes the patient:

- Intraocular surgery in the past 90 days or planned surgery in the next 12 months
- Severe cataract or opacity preventing view to the posterior pole in both eyes
- Chronic hypotony (<5mmHg for ≥90 days) in either eye
- Treatment with oral corticosteroids^a or intraocular corticosteroid injection within the last 12 months
- Use of NSAID eye drops within the last 90 days
- Acute anterior uveitis characterized by redness and symptoms, including but not limited to floaters, pain, and light sensitivity
- Pregnancy or lactation (a pregnancy test will be conducted at baseline and all follow-up visits for females of reproductive age)
- Presence of intraretinal or subretinal fluid in either eye
- Prior safety or tolerability issues with adalimumab
- History of cancer, active tuberculosis, or hepatitis B
- Other medical condition expected to dictate treatment course during the study
- Any of the following laboratory test results on their most recent tests within the past 90 days prior to screening/enrollment^b: leukocyte count <2500, platelet count ≤75000, hemoglobin<9.0, AST or ALT ≥ 2 times the upper limit of normal range, creatinine ≥1.5

Note that patients with acute anterior uveitis, which is often associated with enthesitis-related arthritis including the HLA-B27 positive subtype, are not eligible. Beyond the tests listed above, the remainder of the work-up is at the discretion of the investigator and should be tailored to the clinical situation. Distinguishing between infectious and non-infectious uveitis is part of standard of care and should be dictated by the patient's clinical exam. A prior attempt at discontinuing adalimumab or other TNF-alpha inhibitor is not an exclusion criterion.

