Alternative models with interaction: tests of heterogeneity of effect. Consistency of effect between countries will be investigated. We propose to examine **homogeneity of treatment effect across countries** (by fitting survival models including country as a fixed effect along with treatment-country *interactions*). For the primary model and the aforementioned additional analyses of the primary

model, each will be repeated with an interaction term for country. All such analyses will be made available.

- As a sensitivity analysis, we will exclude treatment failures due to persistent and severe arthritis recurrence and assess the primary model with the recurrence of ocular inflammation only.
- We will examine treatment effect modification by disease type (JIA-associated uveitis vs. CAU) by fitting survival models including disease type as a fixed effect along with a treatment by disease type interaction. A further sensitivity analysis excluding individuals with CAU will be conducted. We acknowledge that these additional analyses may have low power since the trial is powered for main effects (not interaction) and excluding CAU patients will reduce the sample size. These analyses will also be made available.
- **Per-protocol.** We will conduct and report a per-protocol analysis excluding patients who missed 20% or more of their study medication.
- Our design yields failure times at discrete study visits. Statistically, we consider the failure time to occur at the first visit at which it is documented. A sensitivity analysis will be conducted in which we **impute the failure time** at the midpoint of the interval beginning with the last non-failure visit and the first failure visit.

Planned Secondary Analyses

Rationale. The proposed secondary analyses are intended to provide additional scientific information not present in the primary outcome and its analysis. These are of the following types: (1) use of the same outcome variable as the primary outcome, but at (a) different time points or (b) modeled by different covariates, and (2) use of different outcome variables.

- **The time to treatment failure, with censoring at 6 months**, a time to event outcome, will be analyzed using the template in the Primary Analysis above. This is the same outcome as for the primary outcome variable, except with observations restricted to 6 months.

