- **The proportion of people with macular edema.** We anticipate at most 1% of the individuals continuing treatment to develop macular edema, given its absence at baseline. We anticipate approximately 80% power to detect a difference of 15% (in absolute terms) in macular edema in the discontinuation arm (given 118 subjects).

The analyses for censoring at 6 months are similar to 12 months, with small decreases in detectable effect sizes due to assuming slightly shorter follow-up by month 12.

3.3.2.2 Specific Aim 2

Specific Aim 2 is exploratory, and is hypothesis generating. However, we present selected power analyses to illustrate the sufficiency of the sample size of the trial—fixed in Specific Aim 1—to inform regression models of the exploratory outcomes in Specific Aim 2.

For modeling the effect of the potentially predictive biomarker MRP8/14, we assume a

median split as a guide to power. Assuming approximately 50 uveitis flares among our patient population, we anticipate 80% power to detect a difference in MRP8/14 levels of 140 ng/ml (assuming a standard deviation of 250 ng/ml, based on previous studies).^{35,36}

For modeling the number of missed study treatment doses in the first 12 months, we anticipate over 80% power to detect a difference of 2.8 missed doses between the discontinuation and continuation groups (assuming 118 patients enrolled, and a standard deviation of 5).

For the time to failure outcome within 12 months, we anticipate 88% power to detect a hazard ratio of 2.0 between patients taking antimetabolites at baseline and those not using antimetabolites, assuming approximately equal numbers in each group (assuming 10% loss to follow-up).

3.3.2.3 Specific Aim 3

Primary Analysis

The proportion of people who achieved corticosteroid-sparing controlled ocular inflammation (Table 2) by month 6 of the study based on treatment intervention. For sample size planning, we assume a test of proportions between the two randomization groups. Based on prior research, we assume that 30% of those who discontinue adalimumab will have controlled ocular inflammation by month 6.²⁴ We anticipate over 80% power to detect a 29% difference between the two groups, based on 118 subjects.

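### The SAP and the protocol define macular edema differently, and under the SAP wording a stable, thick, dry macula at entry is a treatment failure and not controlled

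*SAP*

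**What the plan says.** **SAP definition.** In SAP 2.3.1, Table 1, one listed feature in one eye is enough for failure. The choroid and retina row includes "macular edema (CST >2 standard deviations above normal thickness or cysts in 1mm central subfield) at a single visit". The table's only baseline footnote belongs to the anterior chamber cell step criterion. SAP 2.3.3, Table 2, repeats the definition for Aim 3, where control requires in both eyes "No active retinal / choroidal lesions or macular edema (CST >2 standard deviations above normal thickness or cysts in 1mm central subfield" (closing bracket omitted).

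**Protocol definition.** Protocol 3.1 starts from the same 2 SD threshold (over 320 µm on Spectralis, over 300 µm on Zeiss or Topcon) but adds "and having a greater than 20% increase from baseline", and/or intraretinal or subretinal fluid, without restriction to the central 1 mm.

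**Which governs.** Protocol Section 3 opens with "See the Statistical Analysis Plan (SAP) for details about the objectives, endpoints, and analysis". Protocol 4.1 points back to Protocol Section 3 for the primary endpoint. On timing, SAP 3.1.1 states "we consider the failure time to occur at the first visit at which it is documented".

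**Entry.** Control at entry (Protocol 5.1) limits cell and haze "and no active retinal/choroidal lesions in either eye", and says nothing on thickness or edema. Protocol 5.2 excludes "Presence of intraretinal or subretinal fluid in either eye". No central subfield thickness (CST) limit is set.

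**Planning.** SAP 3.3.2.1 assumes that at most 1% of the continuing arm develops macular edema, "given its absence at baseline".

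**The concern.** The primary endpoint has two current definitions and no rule for choosing between them. Applied as written, the SAP version has three consequences for an eligible patient whose macula is thick, dry and unchanged since entry:

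1. The patient is a treatment failure at the first follow-up OCT, in either arm.
2. The patient, controlled by the entry definition, is not controlled for Aim 3 while the thickness persists. The time-to-control analyses added after the interim (SAP 3.1.3) use the same Table 2 criteria.
3. The patient counts in the macular edema proportion, although that outcome was planned on edema being absent at baseline.

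Such events are unrelated to treatment and fall early in both arms. They pull the hazard ratio toward 1 and raise the failure rate on continued adalimumab. The distortion is largest, relative to the true rate, if few patients on drug truly fail.

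**Working it through.** **The definitions side by side.** The protocol's and/or can be grouped two ways. Reading A is (CST >2 SD and >20% rise) or fluid. Reading B is CST >2 SD and (>20% rise or fluid). Cysts are taken here as intraretinal fluid.

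| Finding in one eye | Protocol, A | Protocol, B | SAP |
|---|---|---|---|
| CST above cut-off, unchanged, dry | no | no | **yes** |
| CST above cut-off, >20% rise, dry | yes | yes | yes |
| CST below cut-off, cysts in central 1 mm | yes | no | yes |
| CST below cut-off, subretinal fluid only, or fluid outside central 1 mm | yes | no | no |

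The first row differs from the SAP under both readings. The last two depend on the grouping. In the last row the SAP is narrower than the protocol only if fluid alone suffices.

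**The plan's own power.** Inputs from SAP 3.3.1: medians 10 and 20 weeks, 59 per arm, 10% loss, two-sided alpha 0.05; T = 48 weeks. The SAP formula is N = (Zα+Zβ)²(φ(λC)+φ(λI))/(λI−λC)², with φ(λ) = λ²/(1−e^(−λT)), λI = ln2/10 and λC = ln2/20. With 59 × 0.9 = 53.1 per arm it gives power 0.881, so the stated 88% is reproduced.

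**Share affected (assumption).** If CST follows the reference normal distribution, P(>2 SD) = 1 − Φ(2) = 0.0228 per eye. For either of two independent eyes it is 1 − (1 − 0.0228)² = 0.045. In patients: 118 × 0.0228 = 2.7 and 118 × 0.045 = 5.3. Per arm: 59 × 0.0228 = 1.4 and 59 × 0.045 = 2.7. Previously inflamed eyes could differ.

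**Primary endpoint if failures were derived from SAP Table 1.** Simulation at the design rates: exponential failures seen at weeks 4, 8, 12, 16, 24, 32, 40 and 48; dropout hazard 0.0022 per week; Cox model with Efron ties; 59 per arm; 3,000 trials. A fraction f of each arm is made to fail at week 4.

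| f | Median HR | Power |
|---|---|---|
| 0 | 1.990 | 0.927 |
| 0.023 | 1.967 | 0.923 |
| 0.045 | 1.943 | 0.912 |

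Power at f = 0 exceeds 88% because dropouts contribute time until censoring instead of being removed outright. Only the change across rows matters. A separate simulation in continuous time gave the same picture (mean HR 2.02, 1.98 and 1.96).

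**Continuing-arm failure by 12 months**, p + (1−p)f:
- Design rate, p = 1 − 2^(−48/20) = 0.811: becomes 0.815 and 0.819.
- p = 0.10, assumed for illustration: becomes 0.121 and 0.140.

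**Macular edema proportion.** The SAP plans 80% power for a 15-point difference, 1% against 16%. With 53 per arm this gives 0.80, again reproduced. Adding f to both arms gives 0.01 + 0.99f against 0.16 + 0.84f, and power 0.69 (f = 0.0228) or 0.61 (f = 0.045). The planned 1% is 59 × 0.01 = 0.6 patients, while 1.4 to 2.7 per arm would already meet the SAP definition at entry.

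**Aim 3 control at month 12.** For 24% against 24 + 28 = 52% and 53 per arm, power is 0.85. Multiplying both proportions by (1−f) gives 0.84 and 0.83.

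**The case against.** The best reply is that the primary result is protected in practice. Sites declare failure and unmask under Protocol 3.1 and 7.1, SAP 3.1.1 and 3.1.3 refer to failure being declared, and Protocol 4.1 names Protocol Section 3 as the source of the definition. The SAP revision history aligns the single-visit rule with the protocol, which suggests an incomplete carry-over and not a rival endpoint. The Manual of Operations, not available here, may hold the working rule. Much of this stands: if declared failures are analysed, the primary result is unaffected. It does not settle the matter, because SAP 2.3.1 defines recurrence by the Table 1 features and neither document says which text prevails.

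A second reply is that an unchanged thickness is not a recurrence, and that SAP 3.3.2.1 speaks of patients who develop edema. As intent this is plausible. But the Table 1 criterion contains no test of newness, and Table 2 has no such qualifier at all.

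It is also fair that the share is assumed, that the primary effect is small, that the edema proportion is a descriptive outcome (SAP 3.5), and that an absolute thickness limit could be a deliberate, stricter test of control. If the last is intended, the SAP should say so, because it then differs from the entry standard.

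**Conclusion.** The concern holds as a matter of text. Under either reading of the protocol, a thick, dry, unchanged macula is not edema. Under SAP Tables 1 and 2 it is, and eligibility does not keep such patients out.

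For the primary endpoint the likely effect is nil (declared failures) to small (SAP-derived failures: HR 1.99 to 1.94 at most over the assumed range, power down by 1 to 2 points). The wording bears directly on Aim 3 control, including the post-interim time-to-control analyses, and on the macular edema proportion, since the documents describe no site declaration for either. The edema comparison is the most exposed, with power falling from 0.80 to between 0.69 and 0.61.

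All of these sizes rest on the assumed 2.3% to 4.5%. The conflict between the definitions does not. It should be fixed before the final analysis.

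**What to change.** 1. The sponsor confirms whether fluid alone suffices under Protocol 3.1.
2. Put one rule with explicit grouping in the protocol and in SAP Tables 1 and 2, applied eye by eye. If fluid alone suffices: (CST >320 µm on Spectralis or >300 µm on Zeiss/Topcon, and >20% above that eye's baseline) or new intraretinal or subretinal fluid.
3. State that the primary analysis uses failures meeting this rule, and that Aim 3 control and the macular edema proportion use the same rule.
4. Report by arm how many patients are classified differently under the two present definitions. As the interim result is known, settle the rule before making this count.

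The cost is wording and one confirmation. CST and fluid findings are already recorded at baseline and every visit, so the rule needs no new data. Only the count in step 4 might require stored scans to be checked, because cyst location within the central 1 mm is not among the OCT items listed in Protocol 8.1.
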